### **Interviews with PWCIIs**

In-depth interviews (IDIs) will be conducted with PWCI-participants. Interviews will take place after programme completion (6 weeks). Studies evaluating interventions for persons with cognitive impairment a dementia have demonstrated a lasting effect on mood, well-being, and cognitive function for at least a period of 4-6 weeks (Dinius, Pocknell, Caffrey, & Roche, 2023; Ho, Ma, Tan, & Bajpai, 2021), thus participants in the study will be interviewed within 1 month from their programme completion.

Interviews will seek elaboration to participant's short responses to the open-ended questions during the baseline survey interview, such as questions on motivations to attend the programme, perceptions of the museum as a place for older persons, impact on health & well-being, feedback about participation (what they enjoyed, did not enjoy, challenges, benefits) and their experiences being in the museum space (including the Reunion space). The responses will be used to triangulate pre-programme perceptions with post-programme experiences and feedback, as well as ethnographic observations of participants' experiences throughout the entire 6 weeks of programme, to observe for change and account for reasons why changes occur.

Each **in-person** in-depth interview will last for **1 – 1.5 hours** and will take place at a time and place of the participants' convenience and are intended to understand the PWCI-participants' experiences of the programme, including what they find memorable. The interviews are conducted by experienced researcher who are comfortable interacting with older persons, including speaking in their language of choice (E.g. English, Malay, Mandarin, Hokkien, Cantonese, etc.). Interviews will be facilitated by an interview guide which will be translated by the study team.

The IDI will be audio-recorded (with no video-recording), with the consent of the participant, and transcribed for analysis purposes. Each participant will be assigned a unique participant ID, and all identifiable information will be anonymised or removed from any research data at the earliest time possible. Audio-recordings or transcripts from these interviews will be identified only by the unique participant ID which the participant had been assigned during the quantitative baseline survey.

### **Qualitative analysis**

Qualitative data will be analysed thematically using nVivo, a Computer-Assisted Qualitative Data Analysis Software, in accordance with the methods highlighted by Braun & Clarke (2006). Synthesis of both qualitative data and quantitative insights will allow for a better understanding of the configurations of contexts, mechanisms, and outcomes. Thematic analysis provides a well-structured approach to data analysis which is useful for examining the perspectives of diverse research participants (Nowell, Norris, White, & Moules, 2017).

### **Study Sites [Biomedical Research (HBRA) Studies]**

---

- *Please provide the full address(es) (including postal code and unit number) of all premise(s) to be used for the procedures of this study.*
- *Please specify what procedures will be conducted at each of the listed premise(s) and explain why the premise(s) are suitable for the proposed procedures.*
- *Please indicate the applicable type of agreement with the external party for the Non-NUS premises.*

\*required

### **NUS Premises**

---

 Add site

\*required

### **Address**

---

*Please provide the full address(es) (including postal code and unit number) of all premise(s) to be used for the procedures of this study.*

\*required

### Procedures

---

*Please specify what procedures will be conducted at each of the listed premise(s) and explain why the premise(s) are suitable for the proposed procedures.*

Data analysis will be conducted in the CARE office at level 4 in Duke-NUS Medical School, where the study team resides.

---

Add site

---

### Non-NUS Premises

---

Add site

\*required

### Procedures

---

*Please specify what procedures will be conducted at each of the listed premise(s) and explain why the premise(s) are suitable for the proposed procedures.*

- Ethnographic observations of the R&R! programme
- Ethnographic unstructured interviews with NMS staff, and artists
- Casual conversations with PWClIs, Caregivers, volunteers, accompanying staff (from active ageing centres/daycare centres), Artists, NMS staff

This space houses the R&R! programme, the intended unit of study for this research.

\*required

### Type of Agreement

---

*Please indicate the applicable type of agreement with the external party for the Non-NUS premises.*

Research Collaboration Agreement

Service Agreement

Other

\*required

*Please specify.*

---

Project agreement

**Supporting Documents for agreement with the external party for the Non-NUS premises**

---

[2024-0561\\_PA\\_CARE\\_NHB\\_CIE review\\_20240731\\_CARE \(revised\).docx](#)

---

Add site

\*required

### Address

---

*Please provide the full address(es) (including postal code and unit number) of all premise(s) to be used for the procedures of this study.*

Public open spaces (e.g. Void decks, open areas; As indicated/selected by partners or participants)

\*required

## **Procedures**

---

*Please specify what procedures will be conducted at each of the listed premise(s) and explain why the premise(s) are suitable for the proposed procedures.*

- Surveys or Interviews with PWCI

Surveys or interviews may take place in public open spaces, as per the choice of PWCI themselves. These spaces would only be utilised should it be convenient and preferred by the participant themselves.

\*required

## **Type of Agreement**

---

*Please indicate the applicable type of agreement with the external party for the Non-NUS premises.*

Research Collaboration Agreement

Service Agreement

Other

\*required

### **Please specify.**

---

No agreement is provided for use of community open spaces or spaces open to public; permission will be sought from any managing authorities/staff on-site if available

## **Supporting Documents for agreement with the external party for the Non-NUS premises**

---

---

✓ Add site

\*required

### **Procedures**

---

*Please specify what procedures will be conducted at each of the listed premise(s) and explain why the premise(s) are suitable for the proposed procedures.*

- MoCA Screener, consent-taking with PWCIs
- Surveys or Interviews with PWCIs

Active ageing centres (AACs) serve as a recruitment site for PWCIs; AACs often have rooms or spaces which PWCIs and other guests (i.e. the research team) can utilise to conduct interviews, surveys, and assessments in a private and comfortable manner. PWCIs who are recruited from AACs would typically be members of the AAC and have access to the space.

NMS staff and members of the research team will collaborate with the AAC staff for the AACs involved in the study to arrange for the study team's presence at the AAC for MoCA screening and consent-taking, as well as to seek consent to use the space for subsequent study procedures if possible.

AACs not yet confirmed for the study will be added to this IRB application in a future amendment.

The study team will check with IEP on RCA requirements for this study and will commence the study after all necessary agreements are in place.

\*required

### **Type of Agreement**

---

*Please indicate the applicable type of agreement with the external party for the Non-NUS premises.*

Research Collaboration Agreement

Service Agreement

✓ Other

\*required

**Please specify.**

---

NMS Staff has negotiated separately with AAC for use of the space for the MoCA Screener. Permission will be sought from any managing authorities/staff on-site where possible for study procedures beyond initial screening

**Supporting Documents for agreement with the external party for the Non-NUS premises**

---

[2024-0561\\_PA\\_CARE\\_NHB\\_CIE review\\_20240731\\_CARE \(revised\).docx](#)

---

✓ Add site

\*required

## Procedures

---

*Please specify what procedures will be conducted at each of the listed premise(s) and explain why the premise(s) are suitable for the proposed procedures.*

- MoCA Screener, consent-taking with PWCI
- Surveys or Interviews with PWCI

Dementia daycare centres/senior care centres serve as a recruitment site for PWCI; these centres often have rooms or spaces which PWCI and other guests (i.e. the research team) can utilise to conduct interviews, surveys, and assessments in a private and comfortable manner. PWCI who are recruited from this site would typically be members and have access to the space.

NMS staff and members of the research team will collaborate with the dementia daycare/senior care staff for the centres involved in the study to arrange for the study team's presence for MoCA screening and consent-taking, as well as to seek consent to use the space for subsequent study procedures if possible.

Daycare or senior care centres not yet confirmed for the study will be added to this IRB application in a future amendment.

The study team will check with IEP on RCA requirements for this study and will commence the study after all necessary agreements are in place.

\*required

## Type of Agreement

---

*Please indicate the applicable type of agreement with the external party for the Non-NUS premises.*

Research Collaboration Agreement

Service Agreement

Other

\*required

### **Please specify.**

---

No agreement is provided for use for this space as it is open to the older persons in the study who utilise this space; permission will be sought from

any managing authorities/staff on-site where possible for study procedures

## **Supporting Documents for agreement with the external party for the Non-NUS premises**

---

[2024-0561\\_PA\\_CARE\\_NHB\\_CIE review\\_20240731\\_CARE \(revised\).docx](#)

---

✓ Add site

\*required

### **Address**

---

*Please provide the full address(es) (including postal code and unit number) of all premise(s) to be used for the procedures of this study.*

Participant Homes (As indicated/selected by partners or participants, with consent)

\*required

### **Procedures**

---

*Please specify what procedures will be conducted at each of the listed premise(s) and explain why the premise(s) are suitable for the proposed procedures.*

- Surveys or interviews with PWCI

Participants can request for surveys or interviews to be conducted in their homes should they wish to. Members of the research team will only do so with participants' express verbal consent to share their contact details which may include their address.

\*required

### **Type of Agreement**

---

*Please indicate the applicable type of agreement with the external party for the Non-NUS premises.*

## Research Collaboration Agreement

### Service Agreement

Other

\*required

**Please specify.**

---

Verbal consent will be sought from participants who request for interviews or surveys to be conducted in their homes.

### **Supporting Documents for agreement with the external party for the Non-NUS premises**

---

[2024-0561\\_PA\\_CARE\\_NHB\\_CIE review\\_20240731\\_CARE \(revised\).docx](#)

---

Add site

---

\*required

### **Anticipated Study End Date**

---

12/31/2026

## Study Participants

\*required

### Human Subject Groups [Biomedical Research (HBRA) Studies]

---

*This project involves the following group(s):*

Healthy Adults

\*required

Target Number

---

14

\*required

Lower Age Limit

---

21

\*required

Upper Age Limit

---

75

---

Healthy unmarried minors <21 years old

Elderly with mental capacity

\*required

Target Number

---

120

\*required

Lower Age Limit

---

\*required

## Upper Age Limit

---

No upper limit is specified for PWCI; older age is not an exclusion criterion for this group; participants are eligible as long as they meet inclusion criteria

\*required

## How will the mental capacity of elderly be screened?

---

### For PWCI:

Prior to initiation of informed consent, the research team will also administer a screener using Montreal Cognitive Assessment (MoCA). MoCA is a test used to detect mild cognitive decline and early signs of dementia (see more at <https://mocacognition.com/>).

PWCI whose MoCA score ranging from less than 27 (if the participant has 10 or more years of education) OR less than 26 (if the participant has less than 10 years of education), but are above 22 are determined to be eligible for the study, and also eligible to undergo the informed consent independently. These thresholds are following the recommendation of MoCA use in Singapore (see 10.11622/smedj.2013220) and draw from studies concerning mental capacity and consent for persons living with cognitive impairment (10.1002/alz.13698; 10.3390/brainsci7100122; 10.1111/jgs.16786; 10.1212/WNL.0b013e3182a05ba5). Any participants with MoCA score outside of these range will not be included in the study.

---

Outpatients: Adults (21 years old and above)

*(If the study specifically targets subjects who visit hospitals or clinics for diagnosis or treatment without staying overnight)*

Outpatients: Unmarried Minors <21 years old

*(If the study specifically targets subjects who visit hospitals or clinics for diagnosis or treatment without staying overnight)*

Deceased Persons

Vulnerable Populations

Individuals who lack mental capacity: Adults (21 years old and above)

Individuals who lack mental capacity: Minors (<21 years old)

\*required

### **Total Number of Study Participants**

---

134

\*required

### **Inclusion Criteria**

---

*Please identify which criterion is applicable for specific group(s) of research subjects.*

#### **For persons with cognitive impairments (PWCIs):**

1. Fulfils the programme recruitment criteria and registers for the programme through NMS' collaborating partners; AND
2. Provides consent for participation in the study personally; AND
3. Willing and able to participate in interviews independently, without proxy; AND
4. Scores between 22 to 27 on the MoCA (or 22 to 26 for participants with less than 10 years of education). These thresholds follow the recommendation of MoCA use in determining mild cognitive impairment and mild dementia in Singapore (Ng et al., 2013) and draw from studies concerning mental capacity and consent for persons living with cognitive impairment (Karlawish et al., 2013; Veretennikoff et al., 2017; Yang et al., 2024; Zietlow et al., 2020)

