**For persons with cognitive impairments (PWCIs):**

1. Whose cognitive impairment status cannot be confirmed by the administered screener; OR
2. Do not give consent to participate in the study; OR
3. Scores below 22 on the MoCA, or above 27 (or 26 for participants with less than 10 years of education); OR
4. Documented or known diagnosis of moderate or severe dementia

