The eligibility criteria for PWCI in these centres to participate in both R&R! and the study will be explained in detail for the participating day care centers. Centres who have eligible participants will receive more information from NMS so as to support their ability to explain the programme and the research to their participants. The respective centres will determine the eligibility of participants under their care (any documented diagnosis of cognitive impairment or dementia will NOT be shared with NMS programme staff or the research team) and invite interested participants for consent to be contacted by a member of the research team for further explanation, a cognitive assessment, and informed consent. Otherwise, participants who are interested may also choose to indicate their interest to sign up for the programme with either the centre in which they participate, or directly by contacting NMS programme staff. Interested participants with a documented or known diagnosis of moderate or severe dementia will also be contacted only for a subsequent run of the programme beyond the study period.

PWCI who express interest in the study will either:

- Be arranged into timeslot, coordinated by their respective centres, for screening and consent-taking at the centre itself; OR
- be asked for their verbal consent to be contacted by members of the research team for follow-up screener and informed consent, at a time and location of their convenience

A member of the study team will arrange for an in-person cognitive assessment for all interested PWCI, utilising the MoCA. PWCI-Participants who score less than 27 (if the participant has 10 or more years of education) OR less than 26 if the participant has less than 10 years of education), and score above 22 points will be considered eligible for the study. Should the PWCI-Participant be willing to participate, the research staff will initiate the informed consent process with the PWCI-Participant using the PIS&CF as a

guide.

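### The protocol gives two incompatible MoCA eligibility windows, so the lowest and highest scores of the wider window are both admitted and refused

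*Protocol*

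**What the plan says.** The MoCA window appears in five places in the protocol.

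- **Inclusion Criteria, criterion 4 for PWCIs:** "Scores between 22 to 27 on the MoCA (or 22 to 26 for participants with less than 10 years of education".
- **Exclusion Criteria, criterion 3 for PWCIs:** "Scores below 22 on the MoCA, or above 27 (or 26 for participants with less than 10 years of education".
- **How will the mental capacity of elderly be screened?, For PWCI:** "MoCA score ranging from less than 27 (if the participant has 10 or more years of education) OR less than 26" with the shorter education, "but are above 22 are determined to be eligible for the study, and also eligible to undergo the informed consent independently". It then adds: "Any participants with MoCA score outside of these range will not be included in the study".
- **Consent Process:** "PWCI-Participants who score less than 27 (if the participant has 10 or more years of education) OR less than 26" with the shorter education, and in addition "score above 22 points will be considered eligible for the study".
- **Programme Recruitment & Quantitative Sampling:** cites 22 out of 30 as the capacity threshold suggested by earlier studies and turns away only scores below 22. It gives no upper limit.

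The capacity-screening section and inclusion criterion 4 both attribute their limits to the Singapore recommendation for MoCA use and to the same group of consent-capacity studies.

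**The concern.** The first two places treat the end scores as eligible. The next two use strict inequalities at both ends, and one of them closes the door on everything else. A person with an end score therefore gets opposite answers depending on which section is followed, and the shared citations do not show which answer was meant.

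The rule carries four decisions:

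1. **Independent consent.** The capacity-screening section makes its window the test of who may consent without help. A person scoring exactly 22 sits on the threshold that the recruitment section cites and is both allowed and not allowed to proceed.
2. **Enrolment.** Exclusion criterion 1 removes anyone "Whose cognitive impairment status cannot be confirmed by the administered screener". That needs a definite ceiling. If the strict version is the intended one, the formal criteria admit people outside the intended range.
3. **Access to the programme.** Under the Consent Process section, people who fail the criteria are deferred to a run after the study period or pointed to other museum programmes.
4. **Baseline.** Component (i) takes the screening MoCA as the pre-programme value of the cognitive measure, so the rule also fixes the range that this baseline can take.

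**Working it through.** No sample-size or power formula applies. The check applies each section's rule to every whole-number score from 0 to 30, separately by education, and compares the admitted sets. The one assumption is that the MoCA is scored in whole points.

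Let *s* be the score and *U* the stated upper figure: 27 with 10 or more years of education, 26 with fewer.

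| Section | Rule as written | 10 or more years | Fewer than 10 years |
|---|---|---|---|
| Inclusion criterion 4 | 22 ≤ *s* ≤ *U* | 22–27 (6 scores) | 22–26 (5 scores) |
| Exclusion criterion 3 | not (*s* < 22 or *s* > *U*) | 22–27 (6) | 22–26 (5) |
| Capacity screening | 22 < *s* < *U* | 23–26 (4) | 23–25 (3) |
| Consent Process | 22 < *s* < *U* | 23–26 (4) | 23–25 (3) |
| Programme Recruitment | *s* ≥ 22, no ceiling | floor 22 | floor 22 |

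**Differences between the two versions**

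- 10 or more years: {22,…,27} minus {23,…,26} = {22, 27}, so 6 − 4 = 2 of 6 scores are in dispute.
- Fewer than 10 years: {22,…,26} minus {23,24,25} = {22, 26}, so 5 − 3 = 2 of 5 are in dispute.
- No score is admitted by the strict version and refused by the other, so the strict window lies wholly inside the wider one.

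**Count by end**

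- Floor: a score of 22 is admitted by three places (both criteria lists and Programme Recruitment) and refused by two (capacity screening and Consent Process).
- Ceiling: a score of 27 (or 26) is admitted by two and refused by two. Programme Recruitment is silent.

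**Possible windows.** Floor and ceiling could be settled separately. Taking floor 22 or 23 with the upper or lower ceiling gives windows of 6, 5, 5 or 4 scores with 10 or more years of education, and 5, 4, 4 or 3 with fewer.

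**Can the wording be read so that it agrees?** Inclusion criterion 4 could be read as leaving out its end points. Exclusion criterion 3 rules that out, because it removes only scores below 22 or above the upper figure; Programme Recruitment likewise turns away only scores below 22. In the other direction, the capacity-screening and Consent Process sections would have to mean the opposite of their strict inequalities at both ends.

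**The case against.** The strongest reply is that the formal inclusion and exclusion lists agree with each other on both limits, that Programme Recruitment supports them at the floor, and that the strict wording occurs only in narrative answers. A reader might take the narrative as loose phrasing and let the criteria lists govern. This has some force at the floor, where three places stand against two. It does not settle the ceiling, where the count is two against two. The protocol nowhere says that the criteria lists prevail, and the capacity-screening section expressly shuts out scores beyond its own range.

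Further objections limit what may be claimed, and they stand:

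- A score of 22 is not left without a rule; it has two conflicting rules. Consent also does not rest on the MoCA alone, since the criteria require personal consent and independent participation, and a witness to consent is described. The discrepancy does not by itself make any consent invalid.
- Members of the study team give the MoCA, not separate centre teams, so different practice between centres is not a supported mechanism. Different practice between individual staff remains possible.
- The counts of 2 in 6 and 2 in 5 are score values, not people.
- The effect on the baseline range carries little weight, and no bias in the pre-post comparison follows from it.

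**Conclusion.** The concern holds. Current text of one document both admits and refuses scores of 22 and 27 for people with 10 or more years of education, and of 22 and 26 for those with fewer. That is 2 of the 6 and 2 of the 5 score values in the wider windows. The result rests only on the wording and on whole-point scoring. The share of the planned 64–120 participants affected cannot be given, because the protocol reports neither a MoCA distribution nor an education split.

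The point must be fixed because a threshold governing enrolment and independent consent contradicts itself, not because of a demonstrated numerical effect on the results. For a person with an end score, enrolling and refusing each depart from some section of the same application. Which limits are right is not judged here.

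**What to change.** The sponsor and the IRB should reconcile Programme Recruitment & Quantitative Sampling, the capacity-screening section, inclusion criterion 4, exclusion criterion 3 and the Consent Process section to a single rule. For each education stratum it should give the lowest and highest admitted whole-number score and say outright whether 22, and 27 or 26, are included. Floor and ceiling both need a decision, without presuming that either present version is correct. The same sentence should then appear in all five places and on whatever sheet staff use to record screening, before any further participant is screened.

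The cost is a wording amendment and a small edit to the screening paperwork. Choosing the narrower window may raise screen failures somewhat; choosing the wider one has no recruitment cost.
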